### **Sample Size**

We request permission to study up to 30 subjects so that we will have 24 evaluable subjects, respectively, with complete sampling at all time periods. Sample size will be divided into 3 groups; young (18-39-year-old) middle (40 – 59-year-old) and older (60 – 75-year-old).

Sample size was determined using of bootstrap analyses and conventional calculations to estimate the pharmacokinetic parameters within the desired level of accuracy. Table 1 shows the results of 1000 bootstrap replications of the original 11 individuals in the pharmacokinetic study, resampled with N = 11 (the original study size) and N = 20. As expected, the estimates are more precise with increasing study size. The mean and 95% confidence intervals are shown for each parameter.

N	Parameter	Mean	95% Confidence Bound		Range	Correction	Corrected Range
			Lower	Upper			
11	Cl1	0.98	0.89	1.08	20%	2.54	50%
	V1	10.2	8.9	11.9	29%		74%
	Cl2	0.21	0.18	0.24	29%		74%
	V2	7.1	6.1	8.1	28%		70%
20	Cl1	0.97	0.95	1.01	7%	1.88	12%
	V1	10.1	9.6	10.6	10%		18%
	Cl2	0.20	0.20	0.21	8%		16%
	V2	7.0	6.7	7.3	8%		16%

**Table 1** Bootstrap parameter estimates of PK model.

The 95% confidence intervals from the bootstrap are corrected to provide a “best” estimate of the true 95% CI using the upper confidence limit (UCL) method of Browne [1]. As described by Whitehead [10], the 95% UCL correction is  $k/\chi_{(0.95,k)}^2$  where k is N-1, the number of degrees of freedom. As seen in Table 1, the parameters estimated for the initial 11 subjects have a reasonable level of certainty (95% CI < 30% of the mean value) for a small study. However, the corrected CI range from the bootstrap for an N=11 study is closer to 70%. A study with 20 subjects will estimate the parameters within a corrected 95% CI range within 20% of the mean estimated value (Table 1, numbers in red). This is sufficient accuracy to inform the subsequent studies.

Sample size in this study is increased to 24 to permit stratifying by age (3 strata), weight (2 strata), and sex. A corrected confidence range less than 20% (Table 1) implies that mixed effect analysis will distinguish covariate effects in the range of 40% in a study with 20 or more subjects. This is the range at which the covariate effect may be clinically consequential. In practice, mixed-effects analysis with NONMEM is often sensitive to covariate effects smaller than predicted by preliminary analyses.

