meaningfully contribute to accuracy in future patients. We will study 24 subjects. Bootstrap analysis indicates that the confidence interval for studies of 20 individuals using the LC/MS assay will determine the PK parameters with a corrected confidence range < 20%. A corrected confidence range less 20% implies that mixed effect analysis will distinguish covariate effects in the range of 40% in a study with 20 or more subjects. This is the range at which the covariate effect may be clinically consequential. In practice, mixed-effects analysis with NONMEM is often sensitive to covariate effects smaller than predicted by preliminary analyses. The sample size is increased to 24 to provide stratification by age (3 strata), weight (2 strata), and sex. The crossover design permits accurate determination of i.n. bioavailability and dose linearity despite expected high inter-subject variability in absorption.

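### The N=11 and N=20 blocks of Table 1 cannot be reconciled as bootstraps of the same 11 subjects, so the corrected range below 20% and the 40% covariate statement are not supported as written

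*Combined protocol and SAP*

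**What the plan says.** The Sample Size section describes one scheme for the whole of Table 1: 1,000 bootstrap replicates drawn from the 11 pilot subjects, "resampled with N = 11 (the original study size) and N = 20". Each block gives a mean, 95% bounds, the range as a percentage of the mean, a correction factor (2.54 at N=11, 1.88 at N=20) and a corrected range.

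The only comment on the change between blocks is "As expected, the estimates are more precise with increasing study size". The text then says that "the parameters estimated for the initial 11 subjects have a reasonable level of certainty" for a small study, with ranges under 30% of the mean, but that "the corrected CI range from the bootstrap for an N=11 study is closer to 70" percent. For N=20 it concludes: "A study with 20 subjects will estimate the parameters within a corrected 95% CI range within 20% of the mean estimated value".

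The covariate claim is built on this: "A corrected confidence range less than 20% (Table 1) implies that mixed effect analysis will distinguish covariate effects in the range of 40" percent, with 20 or more subjects. The Analytical Plan repeats both statements: "Bootstrap analysis indicates that the confidence interval for studies of 20 individuals using the LC/MS assay will determine the PK parameters" with a corrected range below 20%, and "A corrected confidence range less 20% implies that mixed effect analysis will distinguish covariate effects in the range of 40" percent. The planned number of evaluable subjects is 24, for which no bootstrap result is shown.

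**The concern.** If both blocks come from the same 11 subjects and differ only in resample size, the standard error of each estimate falls roughly as 1/sqrt(N). Going from 11 to 20 should narrow an interval by about a quarter. Table 1 narrows all four intervals by about two thirds or more, and the text presents this as the ordinary effect of a larger study.

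The N=20 block is the only numerical support shown for the stated precision; the text mentions conventional calculations but does not show them. It is also the stated premise for distinguishing covariate effects of about 40%. Assessing age and sex as covariates is the reason the Background gives for stratified recruitment, and covariate effects are listed under the primary outcome. As the table stands, a reader cannot tell what precision to expect for Cl1, V1, Cl2 and V2.

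**Working it through.** **Inputs (Table 1, Sample Size)**

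| | N=11 mean (bounds) | Range | Corrected | N=20 mean (bounds) | Range | Corrected |
|---|---|---|---|---|---|---|
| Cl1 | 0.98 (0.89-1.08) | 20% | 50% | 0.97 (0.95-1.01) | 7% | 12% |
| V1 | 10.2 (8.9-11.9) | 29% | 74% | 10.1 (9.6-10.6) | 10% | 18% |
| Cl2 | 0.21 (0.18-0.24) | 29% | 74% | 0.20 (0.20-0.21) | 8% | 16% |
| V2 | 7.1 (6.1-8.1) | 28% | 70% | 7.0 (6.7-7.3) | 8% | 16% |

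**Step 1. The plan's own arithmetic within rows.** The factor is k/chi-square(lower 5% point, k) with k = N-1. It gives 2.538 at N=11 and 1.878 at N=20, matching 2.54 and 1.88. Ranges, (upper - lower)/mean, and corrected ranges agree with the printed values within the rounding of the bounds. The problem is not here.

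**Step 2. Shrinkage between blocks.** Expected ratio: sqrt(11/20) = 0.742.

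| | Printed range ratio | Largest ratio if bounds are rounded favourably | Implied N = 11/ratio² |
|---|---|---|---|
| Cl1 | 7/20 = 0.35 | 0.07/0.18 = 0.389 | 73 |
| V1 | 10/29 = 0.34 | 1.1/2.9 = 0.379 | 76 |
| Cl2 | 8/29 = 0.28 | 0.02/0.05 = 0.400 | 69 |
| V2 | 8/28 = 0.29 | 0.7/1.9 = 0.368 | 81 |

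The implied N uses the favourable ratio. Requiring agreement with the printed Range and Corrected Range columns as well tightens the largest ratios to 0.34, 0.34, 0.29 and 0.31 (about 94-128 subjects).

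**Step 3. Could chance or non-linear fitting do this?** Bootstrapping the mean of 11 log-normal values (assumed log-scale SD 0.15-0.40, 1,000 replicates, 2,400 data sets) gave an average ratio of 0.74, with all ratios within 0.64-0.84. A second simulation refitted a two-compartment mixed-effects model. It used the N=11 means (units assumed L/min and L), the pilot dosing in the Background (17 µg over 1 min in 3 subjects and over 10 min in 8) and this study's IV sampling times (assumed for the pilot). Two assumed settings were run:

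- between-subject SD 17/25/25/24% with residual 16%;
- between-subject SD 30/40/50/50% with residual 25%.

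With 10 data sets per setting and 400 replicates at each N, mean ratios were 0.73-0.77 and the minimum was 0.61. None of the 80 ratios was at or below 0.40.

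**Step 4. Size if the N=11 block is right.** Raw N=11 ranges from the bounds are 19.4, 29.4, 28.6 and 28.2%. Multiply by sqrt(11/N) and then by the factor (1.878 at N=20, 1.757 at N=24). The square root of the factor (1.370, 1.326) is shown as a milder variant, because an interval width is on the SD scale.

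| | Cl1 | V1 | Cl2 | V2 |
|---|---|---|---|---|
| N=20, plan's factor | 27.0% | 41.0% | 39.8% | 39.2% |
| N=24, plan's factor | 23.1% | 35.0% | 34.0% | 33.5% |
| N=20, square root | 19.7% | 29.9% | 29.0% | 28.6% |
| N=24, square root | 17.4% | 26.4% | 25.6% | 25.3% |
| N=24, square root, N=11 bounds rounded favourably | 16.4% | 25.4% | 20.9% | 23.8% |

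V1, Cl2 and V2 miss 20% in every row. The plan pairs a 20% range with a 40% effect, a 2:1 rule. At N=24 with the plan's factor, that rule gives 2 × 23.1 = 46% for Cl1 and 67-70% for the others.

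**Step 5. Size if the N=20 block is right.** Back-scaling the printed N=20 ranges by sqrt(20/11) × 2.538 = 1.348 × 2.538 = 3.42 gives corrected N=11 ranges of 24.0, 34.2, 27.4 and 27.4%. With the N=20 bounds rounded unfavourably the limits are 24.8, 37.5, 35.1 and 34.5%. The table prints 50, 74, 74 and 70%.

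**The case against.** The strongest counter-argument is that the N=20 rows, taken as printed, do support the claim (12, 18, 16 and 16%), and that the N=11 bootstrap may have been inflated by a minority of unstable fits. That is possible. If unstable replicates are assumed to have four times the normal spread, about 14-15% of them would be needed after favourable rounding of the bounds. At twenty times the spread, about 6% would be enough. On the printed ranges the share runs from about 6% to 27% over the same assumptions. Such fits would also have to be nearly absent at N=20. The plan reports nothing of the kind and attributes the gain to study size alone.

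The refit simulation is limited. It covers 20 data sets with four related parameters each, uses first-order estimation and rests on assumed variances and sampling times. It is not the sponsor's NONMEM run and does not exclude instability specific to that run.

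Two further points stand. The plan offers the 40% figure as a rough expectation and adds that NONMEM often detects smaller effects. And without any correction factor, scaling the N=11 ranges to N=24 gives about 13-20%, so a similar precision statement could be defended on that basis. Both sections, however, rest explicitly on the corrected range.

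Finally, Table 1 contains neither absorption rate nor bioavailability, which are the main objective. That limits the consequence but does not remove the inconsistency.

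**Conclusion.** The concern holds. Under the single scheme the plan describes, the two blocks of Table 1 are incompatible: observed shrinkage is 0.28-0.35 (at most 0.37-0.40 with favourable rounding) against an expected 0.74. All four parameters depart in the same direction, so one misprinted cell does not explain it. The documents do not show which block is wrong, or whether an unreported cause such as unstable N=11 fits accounts for the gap. The corrected range below 20% and the 40% covariate statement are therefore unsupported as written, rather than shown to be false.

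The percentages scaled to N=20 and N=24 are extrapolations that assume 1/sqrt(N) behaviour and a correct N=11 block; they show scale and are not bootstrap results. The consequence is confined to the sample-size justification. Covariates enter the model by the likelihood ratio test and jackknife cross-validation, so no analysis rule, endpoint or safety procedure is affected. This should be fixed, and confidence in the inconsistency is high.

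**What to change.** Re-run the bootstrap at N=11, N=20 and the planned N=24. State the resampling scheme and interval level, report how many replicates converged at each N, and check that widths scale as about 1/sqrt(N). Correct whichever block of Table 1 is wrong, or document the cause of the excess shrinkage. Then replace the precision and covariate sentences in Sample Size and Analytical Plan with what the re-run supports at N=24, using its values and not the extrapolations given here.

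The cost is a re-run of existing code and revised wording in two sections. Enrolment does not change. The only downside is that the stated precision may become less favourable.

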## **Interventions and Interactions**

**Study Visit 1:** The participant will report to the Clinical Research Unit (CRU) of the Wake Forest Clinical Translational Science Institute (CTSI), in the morning after having had nothing to eat or drink since midnight. The participant will review and sign the Informed Consent. After informed consent is adequately obtained, a detailed medical history will be obtained from the participant, female participants will have a urine pregnancy test performed to determine pregnancy status. Vital signs to include blood pressure (BP), heart rate (HR), respiratory rate (Resp) and peripheral oxygen saturation (POX) will be measured and recorded along with height and weight.

Once eligibility has been determined; baseline vital signs (BP, HR, Resp, POX) will be obtained for a baseline measurement and then at the following intervals after the infusion has been initiated; 5, 10, 30, 60, 90 and 120 minutes. Two intravenous catheters will be inserted, one in each arm, and baseline measurements will be obtained. Then 14 µg (8.2 IU) oxytocin (Pitocin®), obtained from the research pharmacy, will be infused over 30 min through one of the catheters. Blood (5 ml) will be sampled from the other catheter at 2, 5, 10, 20, 30, 40, 50, 65, 90, and 120 minutes after the initiation of oxytocin, placed on ice, plasma separated in a refrigerated centrifuge, and stored at -80°C until analyzed for oxytocin concentration. The study will not be blinded. The intravenous catheters will be removed after all data collection and the subject discharged from the CRU. The duration for study visit 2 will be approximately 3.5 hours.

## **Study Visit 2**

On the second visit, the participant will report to the CRU, in the morning after having had nothing to eat or drink since midnight. Baseline vital signs (BP, HR, Resp, POX) will be obtained for a baseline measurement and then at the following intervals after the intranasal oxytocin: 10, 20, 30, 60, 90 and 120 minutes. One intravenous catheter will be inserted. Oxytocin, 102 µg (Tonix-1900, Tonix Pharmaceuticals, Chatham, NJ), obtained from the research pharmacy, will be self-administered in the nasal passages as one metered spray in each nostril followed in 5 min by a second metered spray in each nostril. Blood (5 ml) will be sampled from the IV catheter at 1, 2, 5, 7, 10, 15, 20, 25, 35, 45, and 60 minutes after the initiation of the oxytocin administration, placed on ice, plasma separated in a refrigerated centrifuge, and stored at -80°C until analyzed for oxytocin concentration. The intravenous catheter will be removed after all data collection and the subject discharged from the CRU. The duration for study visit 2 will be approximately 3 hours.

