## Objectives

**Main objective** Model OXT concentrations in plasma after intravenous and i.n. administration in order to determine absorption rate and bioavailability of OXT in plasma after i.n. administration.

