## **STUDY DESIGN**

This is a sequential study of subjects, all of whom will receive, on different occasions, an intravenous infusion or intranasal (i.n.) sprays of oxytocin. Blood samples will be obtained thereafter in order to create a mathematical model to describe the concentrations of oxytocin in the blood over time (pharmacokinetics). In this study, healthy volunteers are recruited for two study drug visits. They will come to the CRU and have two IV catheters inserted, one in each arm for the first study visit. They will receive a 30 minute infusion through one of the IV catheters of oxytocin, 14  $\mu$ g, and blood will be obtained at several times over the next 120 minutes and the amount of oxytocin measured in the blood samples. They will come a second time to the CRU and have one IV inserted in their arm and self-administer i.n. oxytocin, 102 ug over 5 min and blood will be obtained several times over the next 60 minutes and the amount of oxytocin measured in the blood samples. Plasma oxytocin concentrations and individual subject characteristics (age, sex, weight, height, race, and ethnicity) will be analyzed by another group at Stanford University funded under the same NIH grant supporting the work at Wake Forest. The effect of these subject characteristics on the pharmacokinetics of oxytocin will be examined, since these characteristics alter concentration over time of some drugs. Should these characteristics alter oxytocin concentrations, we and others could adjust the dose of oxytocin to the individual.

The main purpose of this study is to sample blood and calculate the pharmacokinetics of oxytocin. We will also assess adverse events during the study.

The research participants will not benefit from this study, but the knowledge we get will be important not only to adjust oxytocin dose to individuals, but to study its possible effects on pain in a more precise way by controlling the amount of oxytocin in the blood circulation. The sample size we chose is needed to get an accurate estimate for the parameters in the pharmacokinetic model for the population in general, not just the subjects in this study.

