**Figure 3. Simulated PK and blood sampling times**

**A)** Simulated plasma OXT concentrations (Cp) with IV infusion. The proposed sampling times (red circles) optimize the informational content to confirm the model generated from 11 subjects in an earlier study.

**B)** Simulated plasma OXT concentrations (Cp) with I.N. self-administration. The proposed sampling times (red circles) optimize the informational content to capture the absorption rate constant. The simulated model assumed a Cmax of 15 min and 1% bioavailability.

The effect of these subject characteristics on the pharmacokinetics of oxytocin will be examined, since these characteristics alter concentration over time of some drugs. Should these characteristics alter oxytocin concentrations, we and others could adjust the dose of oxytocin to the individual.

The main purpose of this study is to sample blood and calculate the pharmacokinetics of oxytocin. We will also assess adverse events during the study.

The research participants will not benefit from this study, but the knowledge we get will be important not only to adjust oxytocin dose to individuals, but to study its possible effects on pain in a more precise way by controlling the amount of oxytocin in the blood circulation. The sample size we chose is needed to get an accurate estimate for the parameters in the pharmacokinetic model for the population in general, not just the subjects in this study.

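### Cheap improvement: moving two intranasal samples to 90 and 120 min would guard the bioavailability estimate against absorption slower than the assumed 15-min peak

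*Combined protocol and SAP*

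**What the plan says.** The main objective is to model plasma oxytocin in order to "determine absorption rate and bioavailability of OXT in plasma after i.n. administration".

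At Study Visit 2 the dose is "i.n. oxytocin, 102 ug over 5 min" (STUDY DESIGN), given as two sets of sprays 5 min apart. Blood is taken "at 1, 2, 5, 7, 10, 15, 20, 25, 35, 45, and 60 minutes after the initiation of the oxytocin administration". Methods and Measures gives the same times, and the Primary Outcome Measure gives an intranasal time frame of 60 min. Intravenous sampling at Visit 1 runs to 120 min.

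The legend of Figure 3 gives the basis for the intranasal times: "The simulated model assumed a Cmax of 15 min and 1% bioavailability". I read this as a time to peak of 15 min. The legend presents the times as those most informative about the absorption rate constant. No slower case is described, and no precision target for F is given; Table 1 covers disposition parameters only.

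Observation at Visit 2 continues after the last blood sample. Vital signs are taken "at the following intervals after the intranasal oxytocin: 10, 20, 30, 60, 90 and 120 minutes". The section then says "The intravenous catheter will be removed after all data collection and the subject discharged from the CRU" and "The duration for study visit 2 will be approximately 3 hours".

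**The concern.** The sampling window rests on an assumed value of one of the two quantities the trial is meant to estimate. F and the absorption rate constant (ka) are told apart largely by the decline after the peak. If a subject absorbs more slowly than assumed, little of that decline is seen by 60 min, and slow absorption with a higher F looks much like faster absorption with a lower F.

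The Analytical Plan expects wide between-subject variation in absorption. So even if 15 min is right on average, some subjects may fall where the schedule is weak. The subject appears to be in the unit until 120 min anyway, so the remedy may be nearly free.

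**Working it through.** **Inputs.** Table 1, N = 20 means: Cl1 0.97, V1 10.1, Cl2 0.20, V2 7.0 (no units stated; L/min and L assumed). Intravenous dose 14 µg over 30 min; intranasal dose 102 µg as two halves at 0 and 5 min. F 1% (Figure 3 legend). Proportional error 16% (LC/MS assay variance, Background). Detection limit 1 pg/ml (Methods and Measures). My assumptions: first-order absorption, 0.25 pg/ml additive error, and values below 1 pg/ml dropped.

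**Step 1: disposition.** k10 = 0.97/10.1 = 0.0960, k12 = 0.20/10.1 = 0.0198, k21 = 0.20/7.0 = 0.0286 per min. The rates α and β have sum k10 + k12 + k21 = 0.1444 and product k10·k21 = 0.00274. Hence α = 0.1219 and β = 0.0225 (half-lives 5.7 and 30.8 min). The coefficients are A = (α − k21)/[(α − β)V1] = 0.0930 and B = (k21 − β)/[(α − β)V1] = 0.00604 per L.

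**Step 2: the plan's own figure.** Methods and Measures predicts more than 1 pg/ml at 120 min after the intravenous dose. With R = 14,000/30 = 466.7 ng/min, C(120) = R[(A/α)(e^(−90α) − e^(−120α)) + (B/β)(e^(−90β) − e^(−120β))] = 8.1 pg/ml. This agrees.

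**Step 3: intranasal profile.** Each half-dose D = 51,000 ng × F contributes D·ka·[A(e^(−αt) − e^(−ka·t))/(ka − α) + B(e^(−βt) − e^(−ka·t))/(ka − β)], the second shifted by 5 min. ka is solved for each time to peak. Total AUC = F × 102,000/Cl1 = 1,020/0.97 = 1,052 pg·min/ml.

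| Peak (min) | ka (/min) | Cmax (pg/ml) | C60 | C90 | C120 | AUC after 60 min |
|---|---|---|---|---|---|---|
| 15 | 0.0625 | 26.3 | 5.1 | 1.7 | 0.7 | 15% |
| 20 | 0.0283 | 15.9 | 8.0 | 4.1 | 2.1 | 34% |
| 25 | 0.0153 | 10.1 | 7.5 | 5.2 | 3.5 | 54% |
| 30 | 0.0093 | 6.8 | 5.9 | 4.8 | 3.8 | 68% |

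**Step 4: precision.** For one subject, a joint fit of both visits has six log-parameters (four disposition, F, ka). The information matrix is M = Σ JᵀJ/[(0.16C)² + 0.25²], where J is the derivative of C with respect to the log-parameters; the SE of log F is the square root of its diagonal element in M⁻¹. The moved schedule takes 2 and 25 min to 90 and 120 min.

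| Peak (min) | SE log F, plan | SE log F, moved | Correlation of log F and log ka, plan |
|---|---|---|---|
| 15 | 0.08 | 0.08 | −0.27 |
| 20 | 0.12 | 0.08 | −0.75 |
| 25 | 0.23 | 0.10 | −0.93 |
| 30 | 0.40 | 0.16 | −0.98 |

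At a 15-min peak the SE of log ka is 0.10 under the plan and 0.09 when moved. Adding the two samples instead gives almost the same SEs of log F. At F 3% the pattern is nearly unchanged (30-min peak: 0.38 to 0.15).

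**Step 5: concentration scale.** The Background states 80 pg/ml for a 30-min target-controlled infusion of 17 µg. Table 1 in L and L/min gives 17,000/[10.1 + 0.97 × 30 + 7.0(1 − e^(−0.0286 × 30))] = 17,000/43.2 = 393 pg/ml, and 393/80 = 4.9. Repeating Step 4 with concentrations 4.9-fold lower gives these SEs of log F:

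| Peak (min) | F 1%, plan | F 1%, moved | F 3%, plan | F 3%, moved |
|---|---|---|---|---|
| 15 | 0.095 | 0.099 | 0.083 | 0.081 |
| 20 | 0.149 | 0.150 | 0.125 | 0.085 |
| 25 | 0.320 | 0.212 | 0.237 | 0.110 |
| 30 | 0.714 | 0.729 | 0.429 | 0.174 |

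At F 1% on this scale the 90- and 120-min values are 0.35/0.15, 0.83/0.42, 1.05/0.71 and 0.97/0.77 pg/ml at the four peaks, mostly below the limit.

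**The case against.** **The plan works under its own assumption.** This stands. At a 15-min peak nothing is lost by stopping at 60 min. The documents give no evidence of a later typical peak; they say only that absorption will vary between subjects.

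**The analysis is a population fit in 24 subjects.** This also stands. Dividing by √24 = 4.9 and ignoring between-subject variation in F, 0.40 becomes about 0.08 and 0.16 about 0.03, even if every subject peaked at 30 min. Pooling does not remove the dependence on the assumed absorption shape, and the covariate aims draw on individual-level information.

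**Late samples may be unmeasurable.** This is the main limit on the gain. On the lower concentration scale at F 1% the move helps only near a 25-min peak (Step 5). Its worst cost there is negligible, 0.71 to 0.73, and the gain returns at F 3%. Dropping low values is also a hard rule; a censored-data likelihood would recover some information.

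**The times were a deliberate choice.** True, but the stated criterion was the absorption rate constant in one scenario, while F is equally part of the objective.

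A reader might infer that F will be biased low. One illustration, with half the absorbed dose entering at 0.1/min and half at 0.02/min, a single rate fitted, and slightly different error settings, gave a bias of −12% under the plan and −4% to −6% with samples moved. I did not re-run it. The split is arbitrary, and the Analytical Plan does not restrict the model to one absorption rate, so it shows what could happen and does not predict a bias.

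**Conclusion.** This is an inexpensive gain in robustness. A reader might conclude that the trial cannot estimate bioavailability, or will estimate it poorly. The documents do not support that: at the stated 15-min peak the schedule is adequate, the intravenous visit informs disposition in the same subject, and the population estimate is more precise than the per-subject figures.

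What holds is narrower. For subjects peaking at about 25 min or later, ka and F become strongly confounded in 60 min of data. On the Table 1 scale, two later samples cut the per-subject SE of log F by more than half (0.23 to 0.10; 0.40 to 0.16) at no cost to ka at a 15-min peak. The size depends on the assumed units, first-order absorption, F and the error model. The concentration scale matters most, because the Background and Table 1 as read here differ about 4.9-fold.

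That the catheter is still in place at 120 min is an inference. Study Visit 2 ties its removal to the end of data collection, and vital signs run to 120 min, but no clock time is given.

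**What to change.** - Keep 11 intranasal samples and move two, for example 2 and 25 min, to 90 and 120 min. This needs no extra assays, blood or visits, and no longer stay if subjects remain to 120 min as the vital-sign schedule implies. Alternatively add the two samples: 2 × 24 = 48 more assays and 2 × 5 = 10 ml more blood per subject.
- State in Study Visit 2 that the sampling catheter stays in until the 120-min sample.
- Extend the intranasal time frame in the Primary Outcome Measure to 120 min, and align the sampling text in Methods and Measures and STUDY DESIGN.
- State the units of Table 1 and reconcile them with the 80 pg/ml in the Background. Then repeat the intranasal simulation with slower absorption before fixing the times, since the scale decides how much the later samples can add.
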